### 7.8 Concomitant medication(s)/treatment(s)

For any subject taking any medication, including over the counter products, nutraceuticals, or herbal medications at Screening or at any time during the course of the study, an accurate record must be kept in the clinic chart (source documentation) and the CRF. This record should include the name of the drug, the dose, the date(s) of administration, and the indication for use.

Changes in the concomitant medication to treat the burden of the predominantly existing disease of the nr-axSpA symptoms is allowed during the Placebo-Controlled Period of the study under the conditions listed below. A change in the first 12 weeks of the study should be avoided.

**Table 7-1: Concomitant Medications (prior to Baseline and Study Visits)**

Drug class	Dose	Exclusion criteria	Study Visits
Analgesics (including, but not limited to acetaminophen, paracetamol, opiates, or combinations thereof)	Up to maximum approved dose	Any change in stable dose regimen is excluded in the 14 days prior to the Baseline visit.	Any ad hoc (prn) use of analgesics is not permitted within 24 hours prior to any post-Screening visit. An increase or addition in opiates or a combination with opiates is not recommended between Week 0 and Week 12 or within 4 weeks prior to the Week 24 or Week 52 visits.

**Table 7–1: Concomitant Medications (prior to Baseline and Study Visits)**

Drug class	Dose	Exclusion criteria	Study Visits
NSAIDs (including COX-2 inhibitors)	Up to maximum approved dose regimen	Any change in stable dose regimen is excluded in the 14 days prior to the Baseline visit.	Any ad hoc (prn) use of NSAIDs is not permitted within 24 hours prior to any post-Screening visit. Changes in NSAID doses should be avoided between Week 0 and Week 12 or within 4 weeks prior to the Week 24 or Week 52 visits.
Oral corticosteroids	Maximum allowed $\leq 10$ mg daily total prednisone equivalent a	Any change in stable dose used for axSpA in the 28 days prior to the Baseline visit. If a taper of oral corticosteroids is planned this should be completed 14 days prior to Baseline visit.	Maximum allowed $\leq 10$ mg daily total prednisone equivalent a Changes in dose or initiation of corticosteroids (including tapers) should be avoided between Week 0 and Week 12 or within 4 weeks prior to the Week 24 or Week 52 visits.
Corticosteroids (im)	Any dose	Use in the 28 days prior to the Baseline visit.	Corticosteroids (im) must not be used during the study.
Corticosteroids (ia)	Up to maximum approved dose	Use in the 28 days prior to the Baseline visit.	SIJ corticosteroid (ia) injections are not allowed during the study. Peripheral joint injections are permitted.

**Table 7–1: Concomitant Medications (prior to Baseline and Study Visits)**

Drug class	Dose	Exclusion criteria	Study Visits
Corticosteroids (iv)	Up to maximum approved dose	Use in the 28 days prior to the Baseline visit.	Doses of corticosteroids (iv) may be used during the study for acute illnesses as long as the dose is not given within 1 week prior to Week 12, Week 24, or Week 52 and the underlying disease does not present a contraindication to the subject remaining in the study. Indications might include dermatitis, gastroenteritis, asthma exacerbation, and pneumonia.
Hyaluronic acid (ia)	Any dose	Use in the 28 days prior to the Baseline visit.	Used in knee as needed after Week 12 visit.
SAARDs b : SSZ and/or HCQ and/or MTX and/or LFN and/or AZA	Maximum allowed: SSZ ≤3g daily HCQ ≤400mg daily MTX ≤25mg weekly AZA ≤150mg/day LFN ≤20mg/day	SAARD initiated and or any change in the dose regimen in the 28 days prior to the Baseline visit.	Changes in SAARD doses should not be made between Week 0 and Week 12 or within 4 weeks prior to Week 24 or Week 52 visit.  SAARD dose reduction to manage intolerance or safety issues is allowed at any time during the study at the Investigator's discretion.
SAARDs: cyclosporine, cyclophosphamide, mycophenolic acid, apremilast	Up to maximum approved dose	Use within 28 days prior to the Baseline visit	Changes in SAARD doses or initiation of a new SAARD should be avoided between Week 0 and Week 12 or within 4 weeks prior to Week 24 or Week 52 visit

**Table 7–1: Concomitant Medications (prior to Baseline and Study Visits)**

Drug class	Dose	Exclusion criteria	Study Visits
Anti-TNF therapies IFX ADA ETN GOL CZP	Any dose	Only 1 previous biologic is allowed. For IFX, ADA, and GOL, any use within the 3 months prior to the Baseline visit. For ETN, use within the 28 days prior to the Baseline visit. For CZP any exposure history.	If biologic therapy is required the subject must be discontinued from study medication, and should conduct the remaining visits according to Figure 5–2 .
Other rheumatologic therapies: ABA rituximab anti-IL17 tocilizumab ustekinumab tofacitinib biosimilars to any approved biologic	Any dose	Any exposure history.	If other rheumatologic therapies are required the subject should be discontinued from study medication and should conduct the remaining visits according to Figure 5–2 .
Osteoporosis medications: eg, risedronate alendronate ibandronate denosumab cathepsin K inhibitor cinacalcet calcitonin	Up to maximum approved dose	All stable osteoporosis medications are permitted except for bisphosphonates (iv).	If the treatment is initiated during the study, the subject should be discontinued from study medication and should conduct the remaining visits according to Figure 5–2 . Osteoporosis medications with the exception of bisphosphonates (iv) are allowed without restriction. Bisphosphonates (iv) are not permitted any time within the study.

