### 6.3 Withdrawal criteria

Subjects are free to withdraw from the study at any time, without prejudice to their continued care.

Subjects should be withdrawn from the study if any of the following events occur:

1. Subject develops an illness that would interfere with his/her continued participation.
2. Subject is noncompliant with the study procedures or medications in the opinion of the Investigator.
3. Subject withdraws his/her consent.
4. There is confirmation of a pregnancy during the study, as evidenced by a positive pregnancy test (see [Section 12.1.6](#) for more information regarding pregnancies).
5. The Sponsor or a regulatory agency requests withdrawal of the subject.
6. Subject's subsequent TB test was confirmed positive or any further evidence is suggestive of potential TB infection (eg, exposure). Refer to [Section 12.6.3](#) for further details and instructions.

Subjects should be withdrawn from the study-treatment if,

7. The Investigator decides to initiate an alternative treatment due to an unsatisfactory response to the study treatment, or
8. Subjects take any of the prohibited medications in [Table 7–1](#) and [Section 7.8.2](#)

If a subject is withdrawn from the double-blind study treatment, the Investigator should encourage the subject to continue participation in the study in accordance with the appropriate alternative schedule of study assessments ([Table 5–2](#) or [Table 5–3](#)). The treatment that the subject receives following withdrawal of study medication is at the discretion of the Investigator,

with open-label CZP available as a treatment option according to the local requirement mandated in the region. UCB will provide this medication free of charge. Alternatively, the Investigator may treat the subject with other treatments (including biologics) as deemed appropriate by local regulations. If the Investigator chooses to withdraw subjects on the other therapy, the local guidelines on initiation and monitoring of the particular treatment should be followed.

Investigators should contact the Medical Monitor, whenever possible, to discuss the withdrawal of a subject from the double-blind study treatment in advance. The reason for discontinuation of the double-blind study treatment must be recorded in the case report form (CRF) as appropriate.

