**Table 7–1: Concomitant Medications (prior to Baseline and Study Visits)**

Drug class	Dose	Exclusion criteria	Study Visits
Intravenous bisphosphonates: zoledronic acid ibandronate pamidronate	Any dose	Zoledronic acid: any use within the 3 years prior to randomization  Ibandronate or pamidronate: any use within the past 2 years.	If iv bisphosphonate treatment is initiated during the study, the subject should be discontinued from study medication and should conduct the remaining visits according to Figure 5–2.

ABA=abatacept; ADA=adalimumab; axSpA=axial spondyloarthritis; AZA=azathioprine; COX-2=cyclooxygenase 2; CZP=certolizumab pegol; DMARD=disease-modifying antirheumatic drug; ETN=etanercept; GOL=golimumab; HCQ=hydroxychloroquine; IFX=infliximab; ia=intra-articular; IL=interleukin; im=intramuscular; iv=intravenous; LFN=leflunomide; MTX=methotrexate; NSAID=nonsteroidal anti-inflammatory drug; RA=rheumatoid arthritis; SAARD=slow-acting antirheumatic drug; SIJ=sacroiliac joint injection; SSZ=sulfasalazine; TNF=tumor necrosis factor

a A table of corticosteroid equivalent doses can be found in Appendix 18.3.

b Throughout the text, we refer to compounds such as SSZ and MTX as SAARDs. These medications are also commonly referred to as DMARDs, but since there is no evidence that they are in fact disease-modifying in axSpA (unlike in RA), we have opted for the more appropriate SAARD terminology.

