### **7.8.2 Prohibited concomitant and rescue treatments (medications and therapies)**

Prior medication exclusions and washout periods are listed in Section 6.2. In addition, use of the following concomitant medications is prohibited during the study, except where indicated:

- Corticosteroids (administered iv/intra-articular [ia]) are permitted only as described in Section 7.8.1. Intramuscular and sacroiliac joint injection (SIJ) ia corticosteroids are not permitted.
- Hyaluronic acid is permitted for the use in the knee after Week 12.
- Biologicals (TNFi: IFX, ADA, ETN, GOL, abatacept (ABA), commercially available CZP), anti-CD20, tocilizumab, ustekimumab, also any other biological response modifiers are excluded.
- All iv bisphosphonates are excluded.

If the subject requires any of the medications specified in this section, the subject must be discontinued from the study treatment prior to the initiation of these medications. Before starting these therapies the Investigator should contact the Study Physician.

If the subject is discontinued from study treatment in order to initiate other treatments (including biologics), the subject will be encouraged to return to the site for future study visits to continue to collect data important for study integrity.

If the subject initiates therapy with CZP, UCB will supply the subject with CZP. If the decision is made to start a different therapy, UCB will not supply such medication.

Subjects must not participate in any other clinical study for any indication or receive any unauthorized medication during the study period.

The administration of live vaccines is not recommended for subjects treated with TNFi. Live vaccines should not be administered 8 weeks prior to Baseline. If immunization with a live organism based vaccine is considered during the study, the clinician is urged to carefully weigh the risks versus benefits of immunization. If the subject is going to proceed with live organism based immunization, the subject must be withdrawn from the study prior to administration of the vaccine. Such vaccines must be recorded in the respective section of concomitant module of the CRF.

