### **14.3 Planned efficacy analyses**

The primary efficacy variable measurement for this study is based on ASDAS-MI response at Week 52. The associated primary outcome of the study will be defined as a composite endpoint that is achieved if a subject fulfills the following 2 components:

1. Remain in the study and on the double-blind study treatment through 52 weeks
2. Achieve an ASDAS-MI response at 52 weeks

For simplicity, this primary efficacy variable will be referred to as ASDAS-MI response at Week 52. However, the composite definition as described above will apply when this endpoint is analyzed. The primary analysis for this endpoint will be based on logistic regression. The odds ratio of the ASDAS-MI responder rates at Week 52 will be estimated and tested between treatment groups using a logistic regression model with factors of treatment group, region, and MRI/CRP classification (MRI+/CRP+; MRI+/CRP-; MRI-/CRP+). If the logistic regression

model is unable to converge, then the MRI/CRP classification variable may be dropped from the model to facilitate convergence. The study design is likely to result in some sites with a small number of enrolled subjects. The use of region as a stratification variable and as a factor in the model is intended to combine study centers in similar geographic regions. The geographic regions to be used will be defined in the IXRS and in the SAP. Given the composite endpoint definition described above, there will be no missing data for the primary endpoint, as subjects that discontinue the double-blind study treatment prior to Week 52 or who do not have an ASDAS-MI status at Week 52 are considered nonresponders to the double-blind study treatment.

As described in Section 6.3, subjects who discontinue the double-blind study treatment will not necessarily be withdrawn from the study. In an attempt to minimize missing data, efforts will be made to continue to collect safety and efficacy data on these subjects through study completion. Sensitivity analyses will be performed to evaluate the impact of missing data on the analysis of the primary efficacy variable (see Section 14.8).

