## 14.10 Determination of sample size

Subjects will be randomized in a 1:1 ratio to the CZP 200mg Q2W and placebo treatment groups. The expected responder rates for ASDAS-MI at Week 52 are 40% and 20% for CZP and placebo, respectively. A total sample size of 300 (150 subjects per treatment group) provides 95% power to detect a statistically significant difference in the ASDAS-MI responder rate at Week 52 between CZP and placebo, using a 2-sided significance level of 0.05.

With Protocol Amendment 4, ASAS40 response at Week 12 was elevated to be the primary efficacy variable for Canada (and any other country where applicable or where requested by Regulatory Authorities); however, the study was fully enrolled at the time of this amendment. The expected responder rates for ASAS40 response at Week 12 are also 40% for CZP and 20% for placebo, which are identical to the assumed response rates cited for ASDAS-MI at Week 52. Therefore, the planned total sample size of 300 would provide 95% power for this variable, as well.

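### The osteoporosis row of Table 7–1 tells sites both to stop study medication when treatment is started and to allow every non-iv osteoporosis drug without restriction

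*Protocol*

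**What the plan says.** The osteoporosis row of Protocol Table 7–1 covers the class in general. Its examples include risedronate, alendronate, ibandronate, denosumab and calcitonin. The Study Visits cell gives three instructions in sequence:

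- "If the treatment is initiated during the study, the subject should be discontinued from study medication", with the remaining visits to follow Figure 5–2.
- "Osteoporosis medications with the exception of bisphosphonates (iv) are allowed without restriction".
- "Bisphosphonates (iv) are not permitted any time within the study".

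The exclusion cell of the same row permits stable osteoporosis drugs at entry, iv bisphosphonates excepted.

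The following row deals with iv bisphosphonates alone: "If iv bisphosphonate treatment is initiated during the study, the subject should be discontinued from study medication". Section 7.8.2 lists prohibited treatments, and its only osteoporosis entry is "All iv bisphosphonates are excluded".

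Section 6.3, criterion 8, ends study treatment when "Subjects take any of the prohibited medications in" Table 7–1 and Section 7.8.2. Section 14.3 counts as non-responders "subjects that discontinue the double-blind study treatment prior to Week 52".

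**The concern.** The first sentence of the cell is a stopping rule with no drug named. Under a row heading that covers osteoporosis drugs generally, it reads as applying to any of them. The second sentence removes all restriction from every osteoporosis drug except the iv bisphosphonates. For a newly started oral bisphosphonate or denosumab, the two give opposite instructions.

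What is at stake is whether a site ends blinded treatment:

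- **Primary endpoint.** A site that follows the first sentence makes the subject a non-responder on the Week 52 composite, whatever the ASDAS. A site that follows the second keeps the subject on treatment, and the ASDAS decides.
- **Continuous secondary endpoints.** Under Section 14.4, values after discontinuation are replaced by imputation from a placebo-based model.
- **The subject.** The Figure 5–2 path leads to open-label CZP or another treatment. Section 6.4 bars subjects on alternative treatments from the extension.

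Two sites could handle identical subjects differently and each cite the same cell. The endpoint rule in Section 14.3 is itself clear. The fault lies in the instruction that feeds it.

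**Working it through.** **Textual check.** Take a subject who starts a non-iv osteoporosis drug before Week 52.

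| Source | Instruction for that subject |
|---|---|
| Table 7–1, osteoporosis row, first sentence | Discontinue study medication |
| Table 7–1, osteoporosis row, second sentence | Drug allowed, no restriction |
| Table 7–1, iv bisphosphonate row | Does not apply |
| Section 7.8.2 | Drug not listed as prohibited |

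Three milder readings were tried.

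1. *The unnamed treatment means iv bisphosphonates only.* The cell does not say so, and the row heading is the whole class. The next row states the same rule with the qualifier that is missing here. Ibandronate appears in both rows, so the qualifier matters in practice.
2. *The second sentence covers only drugs already stable at Baseline.* The word stable is in the exclusion cell, not in the Study Visits cell. Losing study treatment for any new start is a restriction, so the conflict remains.
3. *The text is superseded.* The Table 7–1 changes logged in Amendment 1 (Change #33) show only the SAARD and anti-TNF rows. The osteoporosis wording is in the current table.

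**Size.** The protocol does not say how many subjects start such drugs, so the calculation is per subject. Inputs from Section 14.10: 150 per arm, two-sided 0.05, and "The expected responder rates for ASDAS-MI at Week 52 are 40% and 20% for CZP and placebo, respectively".

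- Expected responders: 0.40 × 150 = 60 on CZP; 0.20 × 150 = 30 on placebo.
- One responder lost: 1/150 = 0.67 percentage points of that arm's rate. That is 1/60 = 1.7% of expected CZP responders, or 1/30 = 3.3% of expected placebo responders.

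Power for two proportions is Φ[(d − 1.96 × SE0)/SE1]. Here d is the difference in rates, SE0 = √(2p̄(1 − p̄)/n) and SE1 = √((p1(1 − p1) + p2(1 − p2))/n).

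- *As planned, 60/150 against 30/150:* p̄ = 0.30, SE0 = 0.05292, SE1 = 0.05164. The argument is (0.2000 − 0.1037)/0.05164 = 1.865, so power is 96.9%. The protocol states 95% and does not name its formula. Subtracting a continuity correction of 1/150 from d gives (0.1933 − 0.1037)/0.05164 = 1.736, or 95.9%. Both results are in line with the stated figure.
- *One CZP responder lost, 59/150 against 30/150:* d = 0.1933, SE0 = 0.05275, SE1 = 0.05155. The argument is (0.1933 − 0.1034)/0.05155 = 1.745, so power without the correction is 96.0%, a fall of about 0.9 points.
- *One responder lost in each arm, 59/150 against 29/150:* the difference is still 30/150 = 20 points.

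**The case against.** The strongest reply is that the cell separates new starts from continued use. On that view the first sentence governs initiation, the second governs drugs already being taken, and it is not certain which sentence is the mistake. It is fair that the sponsor's intent is inferred. But the second sentence says there is no restriction at all, so this reading does not reconcile the two, and one of them has to change either way.

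Two of the supports are weaker than they look. Criterion 8 in Section 6.3 points to Table 7–1 as well as to Section 7.8.2, so using it to show that the table does not prohibit these drugs is partly circular and adds little. The list in Section 7.8.2 may not be exhaustive. The direction of the fix rests mainly on the iv bisphosphonate row, with Section 7.8.2 in support.

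Text displaced when the table was read from the PDF is possible but not shown. The row above has its own complete discontinuation sentence.

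The points about consequence largely stand:

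- Section 6.3 asks investigators to contact the Medical Monitor, where possible, before withdrawing a subject from blinded treatment, which would catch some cases.
- Discontinued subjects are followed to Week 52, and Section 14.8 plans a sensitivity analysis on observed Week 52 data regardless of treatment. That analysis does not restore the blinded comparison for a subject who has switched to open-label CZP.
- The ambiguity applies to both arms, and nothing in the protocol suggests it would act differently between them.
- Section 2.2 says axSpA typically presents before age 45, so new osteoporosis treatment within a year should be uncommon.
- Section 14.10 says the study was fully enrolled by Amendment 4, so a correction now would reach only subjects still in the Double-Blind Period, a number the protocol does not give.

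**Conclusion.** The concern holds. The cell contradicts itself for any newly started non-iv osteoporosis drug, and no reading that was tried removes the conflict. The iv bisphosphonate row and Section 7.8.2 indicate that discontinuation was meant for iv bisphosphonates only.

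The effect on the primary analysis is minor. The power figures assume the planning rates of 40% and 20%, 150 subjects per arm, the uncorrected pooled-variance formula, and the loss of exactly one CZP responder with none lost on placebo. They illustrate scale and do not predict a count. The reason to correct the text is that it is an operative stopping rule, with a direct route to avoidable non-response and to inconsistent handling between sites.

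**What to change.** In the Study Visits cell of the osteoporosis row of Table 7–1, delete the opening discontinuation sentence, or name iv bisphosphonates in it as the next row does. Starting a non-iv osteoporosis drug would then not end blinded treatment, and Table 7–1 would agree with Section 7.8.2. If the sponsor did intend new non-iv treatment to end study medication, the sentence to rewrite is the one that lifts all restriction, and those drugs should be added to Section 7.8.2.

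Either way the cost is a small wording change, with no added data, visits or subjects. If it comes too late for subjects in the Double-Blind Period, a check for any discontinuations attributed to starting an osteoporosis drug would show whether the wording had any effect.

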**Table 7–1: Concomitant Medications (prior to Baseline and Study Visits)**

Drug class	Dose	Exclusion criteria	Study Visits
Intravenous bisphosphonates: zoledronic acid ibandronate pamidronate	Any dose	Zoledronic acid: any use within the 3 years prior to randomization  Ibandronate or pamidronate: any use within the past 2 years.	If iv bisphosphonate treatment is initiated during the study, the subject should be discontinued from study medication and should conduct the remaining visits according to Figure 5–2.

ABA=abatacept; ADA=adalimumab; axSpA=axial spondyloarthritis; AZA=azathioprine; COX-2=cyclooxygenase 2; CZP=certolizumab pegol; DMARD=disease-modifying antirheumatic drug; ETN=etanercept; GOL=golimumab; HCQ=hydroxychloroquine; IFX=infliximab; ia=intra-articular; IL=interleukin; im=intramuscular; iv=intravenous; LFN=leflunomide; MTX=methotrexate; NSAID=nonsteroidal anti-inflammatory drug; RA=rheumatoid arthritis; SAARD=slow-acting antirheumatic drug; SIJ=sacroiliac joint injection; SSZ=sulfasalazine; TNF=tumor necrosis factor

a A table of corticosteroid equivalent doses can be found in Appendix 18.3.

b Throughout the text, we refer to compounds such as SSZ and MTX as SAARDs. These medications are also commonly referred to as DMARDs, but since there is no evidence that they are in fact disease-modifying in axSpA (unlike in RA), we have opted for the more appropriate SAARD terminology.

